Amendment number	Date of amendment	Protocol version number	Type of amendment	Summary of amendment

# **Abbreviations and Definitions**

Term		Description						
Adverse E	ivent (AE)	Any untoward medical occurrence in a clinical trial participant administered a medicinal product and which does not necessarily have a causal relationship with this treatment. Comment: An AE can therefore be any unfavourable and unintended sign (including abnormal laboratory findings), symptom or disease temporally associated with the use of an investigational medicinal product, whether or not related to the investigational medicinal product.						
Adverse F (AR)	teaction	Any untoward and unintended responses to an IMP related to any dose administered. Comment: An AE judged by either the reporting Investigator or Sponsor as having causal relationship to the IMP qualifies as an AR. The expression reasonable causal relationship means to convey in general that there is evidence or argument to suggest a causal relationship.						
ALT		Alanine aminotransferase						
ATS		American Thoracic Society						
ATT		Anti-tuberculosis Therapy						
BTA		British Thoracic Society						
DILI		Drug Induced Liver Injury						
DMC		Data Monitoring Committee						
DMP		Data Management Plan						
E		Ethambutol						
EHR		E = ethambutol, H = isoniazid, R = rifampicin						
EHRZ		E = ethambutol, H = isoniazid, R = rifampicin, Z = pyrazinamide						
ЕоТ		End of Treatment						
н		Isoniazid						
ICF		Informed Consent Form						
ICU		Intensive Care Unit						
IMP		Investigational Medicinal Product						
ISF		Investigator Site File						
LFT		Liver Function Test						
LTBI		Latent Tuberculosis Infection						
NCTU		Nottingham Clinical Trials Unit						
NHS		National Health Service						
NICE		The National Institute for Health and Care Excellence						
NIHR		National Institute for Health and Care Research						
PHE		Public Health England						
PI		Principal Investigator						
Trial name:	TB-DILI Trial	Protocol 1.2 date: 02-Aug-2022 Page 7 of 58 version:						

PIS	Participant Information Sheet
PPI	Patient and Public Involvement
QoL	Quality of Life
QALY	Quality Adjusted Life Year
R	Rifampicin
RCT	Randomised Controlled Trial
SAP	Statistical Analysis Plan
Serious Adverse Event (SAE)	
 
Any untoward medical occurrence or effect that:
 
Results in death
 
Is life-threatening*
 
Requires hospitalisation or prolongation of existing hospitalisation
 
Results in persistent or significant disability or incapacity
 
Is a congenital anomaly/birth defect
 
Or is otherwise considered medically significant by the Investigator**
 
Comments: The term severe is often used to describe the intensity (severity) of a specific event. This is not the same as serious, which is based on participants/event outcome or action criteria.
 
* Life threatening in the definition of an SAE refers to an event in which the participant was at risk of death at the time of the event; it does not refer to an event that hypothetically might have caused death if it were more severe.
 
** Medical judgment should be exercised in deciding whether an AE is serious in other situations. Important AEs that are not immediately life threatening or do not result in death or hospitalisation but may jeopardise the participant or may require intervention to prevent one of the other outcomes listed in the definition above, should be considered serious.
 

Serious Adverse Reaction (SAR)	An Adverse Reaction which also meets the definition of a Serious Adverse Event
Source data	All information in original records and certified copies of original records of clinical findings, observations, or other activities in a clinical trial necessary for the reconstruction and evaluation of the trial
Suspected Unexpected Serious Adverse Reaction (SUSAR)	A SAR that is unexpected i.e. the nature, or severity of the event is not consistent with the applicable product information. A SUSAR should meet the definition of an AR, UAR and SAR.
ТВ	Tuberculosis
TMF	Trial Master File
TMG	Trial Management Group
TSC	Trial Steering Committee
ULN	Upper Limit of Normal
Unexpected Adverse Reaction (UAR)	An AR, the nature or severity of which is not consistent with the applicable product information (e.g. Investigator Brochure for an unapproved IMP or Summary of Product Characteristics (SmPC) for a licensed product). When the outcome of an AR is not consistent with the applicable product information the AR should be considered unexpected.

Trial	TB-DILI Trial	Protocol	1.2	date:	02-Aug-2022	Page 8 of 58
name:		version:				

# Pyrazinamide

# TRIAL SUMMARY

Ζ

# (This table shows the summary for the main trial only. For details of the cohort study see Appendix A).

Title	Reintroduction of anti-tuberculosis therapy following drug-induced liver
	injury: a randomised controlled trial
Trial Design	Pragmatic, individually randomised, parallel group, open randomised controlled superiority trial with concealed allocation (1:1) and minimisation
Objectives	
 
Primary objective 
 
To determine if reintroduction of a non-pyrazinamide (Z)-containing anti-tuberculosis therapy (ATT) regimen results in a lower drug-induced liver injury (DILI) recurrence rate compared to a Z-containing ATT regimen in adults who have experienced an episode of DILI when being treated for active tuberculosis (TB)
 
 
 
Secondary objectives 
 
To determine the cost-effectiveness of reintroducing a non-Z containing, versus Z-containing regimen
 
 
 
Cohort study 
 
To determine i) the frequency and ii) quality of life impacts of DILI episodes in adults being treated for latent TB infection
 
 
 

Eligibility criteria	
 
Inclusion Criteria
 
Aged ≥18 years
 
Experienced DILI with standard 4-drug ATT for active pulmonary or extra-pulmonary TB
 
Medically suitable
 
for re-introduction of standard 4-drug ATT
 
Exclusion Criteria
 
Requirement for alternative ATT
 
Unable to provide written informed consent
 

Intervention and control	
 
Intervention         
 
Sequential full-dose reintroduction of a non-Z-containing 3-drug ATT regimen comprising ethambutol, isoniazid and rifampicin (EHR), as recommended by the American Thoracic Society (ATS) TB guideline
 
Control
 
Sequential full-dose reintroduction of a Z-containing 4-drug ATT regimen comprising ethambutol, isoniazid, rifampicin and pyrazinamide (EHRZ), as recommended by the National Institute for Health and Care Excellence (NICE) TB guideline
 
 
 

Trial	TB-DILI Trial	Protocol	1.2	date:	02-Aug-2022	Page 9 of 58
name:		version:				

Outcome	Primary
Measures	
 
DILI recurrence within 12 months following randomisation
 
Secondary
 
Severity of DILI recurrence
 
Physician rated clinical cure at end of treatment (EoT)
 
Clinical cure at 12 months
 
Total number of days on ATT at EoT
 
ATT adherence at EoT
 
Adverse event rate at EoT or at 12 months whichever is sooner
 
Mortality at 12 months
 
Quality of life assessed by EQ-5D-5L and healthcare resource use
 

Sample Size	350 patients recruited across approximately 40 sites
Expected recruitment duration	48 months

ſ	Trial	TB-DILI Trial	Protocol	1.2	date:	02-Aug-2022	Page 10 of 58
	name:		version:				

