# **1.2.1.** Justification for participant population

The target population comprises of adults treated within the NHS for active TB with standard 4-drug ATT who have experienced an episode of DILI requiring these drugs to be stopped.

The main trial will determine the risk of recurrence and health economic impacts of a pyrazinamide (Z)-containing versus non-Z containing reintroduction regime following a DILI episode. Pyrazinamide (Z) is not a component of treatment for latent TB infection (LTBI). Therefore, including patients with LTBI in the main trial is not appropriate. Furthermore, anecdotal evidence suggests DILI occurrence (from treatment with R or H) in these patients, who are usually clinically well, is likely very low (<1.5%). A separate clinical trial to determine the safest and most effective drug reintroduction strategy in these patients is not feasible in the UK because of the very large sample size needed for a definitive study. Instead, we propose a cohort study to provide firmer estimates of the frequency of DILI occurrence and recurrence, and the quality-of-life impacts arising. The cohort study involving patients with latent TB infection (LTBI) will also benefit the current trial because it will keep sites actively recruiting into the programme of research. We provide further details of the cohort study in Appendix A.

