# Aim

The aim of this cohort study will be to determine with greater precision the frequency of DILI recurrence under standard care conditions in the NHS, and the quality of life impacts arising. *If possible,* we will determine independent risk factors for DILI recurrence. (Based on an estimate of 1.5% DILI recurrence, 1300 participants would be required to determine two independent risk factors for DILI recurrence).

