## **Primary outcome**

• DILI recurrence at end of treatment

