## **Eligibility criteria**

## **Inclusion criteria**

- Adult aged  $\geq$  18 years
- Experienced DILI with anti-LTBI drugs
- Medically suitable for re-introduction of anti-LTBI drugs.

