## Sample size and expected recruitment

Annually, of 15,000 patients treated for LTBI in the UK, and based on a DILI occurrence of 1.5%, we may be able to recruit up to 75 participants (33% of eligible patients) per year, but estimates

Trial	TB-DILI Trial	Protocol	1.2	date:	02-Aug-2022	Page 57 of 58
name:		version:				

are highly indeterminate. We propose a pilot phase of 18 months. If pilot data confirm very low DILI occurrence and recurrence, further recruitment may not be justified.

Based on an estimate of 1.5% DILI recurrence, 1300 participants would be required to determine two independent risk factors for DILI recurrence.

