## **Statistical analysis**

Descriptive statistics of demographic and clinical measures will be used to describe the characteristics of participants upon entry to the cohort study. The following outcomes at 12 months will be described descriptively with 95% confidence intervals where appropriate:

a) DILI recurrence,

- b) severity of DILI recurrence,
- c) total number of days on anti-LTBI drugs,
- d) adverse event rate,
- e) quality of Life using EQ-5D and healthcare resource use.

Descriptive statistics of baseline characteristics and DILI severity will be presented for participants with and without a DILI recurrence during the follow-up period. If feasible, an exploratory analysis will employ logistic regression modelling to identify potential candidate risk factors for DILI recurrence.

Trial	TB-DILI Trial	Protocol	1.2	date:	02-Aug-2022	Page 58 of 58
name	:	version:

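### The LTBI cohort is said to estimate how often DILI occurs, and its pilot rule leans partly on that, but it enrols only patients who already have DILI, so only recurrence can be estimated

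*Protocol*

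**What the plan says.** Three places in the protocol treat the cohort as a source for how often DILI occurs:

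- The Trial Summary gives the objective as "To determine i) the frequency and ii) quality of life impacts of DILI episodes in adults being treated for latent TB infection".
- Section 1.2.1 says the cohort will "provide firmer estimates of the frequency of DILI occurrence and recurrence".
- Appendix A, Sample size and expected recruitment, proposes an 18-month pilot and adds: "If pilot data confirm very low DILI occurrence and recurrence, further recruitment may not be justified".

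The rest of Appendix A describes something narrower. Its opening defines the target population as LTBI patients who develop DILI on treatment, and the inclusion criteria require "Experienced DILI with anti-LTBI drugs". The stated aim is the frequency and quality-of-life impact of recurrence, and the primary outcome is "DILI recurrence at end of treatment".

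The secondary outcomes are likewise measured at end of treatment, and the last scheduled EQ-5D-5L is one week after it. The Statistical analysis paragraph nevertheless says: "The following outcomes at 12 months will be described descriptively".

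On size, Appendix A assumes 15,000 LTBI patients treated a year in the UK, 1.5% DILI occurrence and up to 75 recruits a year (33% of those eligible). Separately, at 1.5% recurrence, it says that "1300 participants would be required to determine two independent risk factors for DILI recurrence". That last aim is offered only if possible.

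**The concern.** The frequency of DILI during LTBI treatment is the number who develop DILI divided by the number treated. Everyone in this cohort has had DILI at entry, so the enrolled group holds no one at risk of a first episode. The objective in the Summary and section 1.2.1, and the occurrence half of the pilot rule, therefore rest on a quantity that the described data collection does not produce.

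Section 1.2.1 offers the cohort in place of a trial that it judges infeasible because DILI in this population is thought to be rare, on anecdotal evidence. If the cohort cannot firm up that figure, part of its stated justification falls away. There is also a risk that recruited cases over some convenient national total would later be reported as an occurrence rate.

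Two smaller matters sit alongside. A primary outcome with two time points leaves the estimand open. And a recurrence rate with no basis of its own makes it hard to judge what the pilot or the optional risk-factor analysis can deliver.

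**Working it through.** **1. Is there a denominator for occurrence?**

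- *Enrolled participants:* all have had DILI (Appendix A, opening and inclusion criteria). They supply cases only.
- *Screening summaries* (section 5.1, carried over to the cohort by Appendix A's reference to section 5): these could yield a count of DILI cases, but nothing says that LTBI treatment starts are to be counted.
- *Routine-data consent for those who do not enter* (section 5.3): this reaches potential participants, that is, people who already have DILI.
- *The 15,000 in Appendix A:* a UK planning figure, not the number treated at participating sites.

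None gives the number treated where the cases arise.

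**2. Recruitment figures, reproduced.**

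- Eligible per year: 15,000 × 0.015 = 225.
- Recruited at 33%: 225 × 0.33 = 74.25; the stated 75 is 75/225 = one third. The protocol's figure reproduces.

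**3. Would a denominator alone be enough?** No. With recruited participants as numerator, 75/15,000 = 0.5%, against the assumed 225/15,000 = 1.5%. That is a threefold understatement, because two thirds of eligible patients are not expected to join. Patients with DILI who are unsuitable for reintroduction are not eligible at all (inclusion criteria) and would be missed too.

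**4. What the pilot can say about recurrence.** Eighteen months at 75 a year is 75 × 1.5 = 112.5 participants. At 1.5% recurrence the expected number of events is 112.5 × 0.015 = 1.7. For illustration, 2 recurrences in 112 has an exact (Clopper-Pearson) 95% confidence interval of 0.2% to 6.3%.

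**5. The 1300.** The protocol gives no formula. Assuming 10 events per candidate factor, 2 × 10 / 0.015 = 1333, close to 1300 (1300 × 0.015 = 19.5 events). Assuming 5, 15 or 20 events per factor gives 667, 2000 or 2667, none of which matches.

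The time needed depends heavily on the recurrence rate. The 5% and 10% rows are assumed values for sensitivity, not protocol figures for LTBI. The last column assumes that the cohort runs for the main trial's 48 months (section 3.2), which Appendix A does not say; that gives 75 × 4 = 300 participants.

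| Recurrence | Participants needed | Years at 75 a year | Recurrences in 300 |
|---|---|---|---|
| 1.5% (protocol) | 1300, as stated | 1300/75 = 17.3 | 4.5 |
| 5% (assumed) | 20/0.05 = 400 | 400/75 = 5.3 | 15 |
| 10% (assumed) | 20/0.10 = 200 | 200/75 = 2.7 | 30 |

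Because 75 is an upper limit, each duration is a minimum at its rate.

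**6. Two uses of 1.5%.** In Appendix A it is the occurrence among all treated LTBI patients and also the recurrence among those who have had DILI. These are different populations and different risks. Section 1.2.1 gives an anecdotal figure below 1.5% for occurrence; no source is given for recurrence after DILI on LTBI treatment.

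**7. Time point.** The primary and secondary outcome lists say end of treatment; the Statistical analysis paragraph lists the same outcomes at 12 months. With the last EQ-5D-5L one week after end of treatment, no 12-month quality-of-life measurement is scheduled.

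**The case against.** The best defence is that Appendix A governs. The Summary table says that it covers the main trial and refers the reader to Appendix A, whose population, aim, primary outcome and inclusion criteria agree with one another and concern recurrence. That stands as far as it goes: the cohort's primary question is answerable. It does not remove the conflict, because the Summary still prints the objective, section 1.2.1 repeats it in the body, and Appendix A itself brings occurrence into the pilot rule.

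A reader might infer that the pilot decision cannot be made at all. The text does not support that. The rule is softly worded, it names recurrence too, and the pilot can observe recurrence, if imprecisely. Only the occurrence half is unsupported.

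A reader might also infer that the cohort is undersized by some 17 years of recruitment and that the risk-factor regression should be struck out. That goes too far. The 1300 is not a recruitment target. The risk-factor aim is conditional, the regression is called exploratory and is to be run only if feasible, and the protocol admits that its recruitment estimates are highly indeterminate. The 17 years also rests on the 1.5% recurrence figure, which is itself without a stated basis.

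On the time point, section 14.2.2 takes the risk of DILI after the drugs stop as zero in the main trial. If that carries over, the choice would change the recurrence count little for patients who have finished treatment by 12 months. The conflict remains for quality of life and for the definition of the outcomes.

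**Conclusion.** The protocol contradicts itself on what the cohort estimates. As designed, it can estimate recurrence and quality of life among LTBI patients who have had DILI; it cannot estimate how often DILI occurs during LTBI treatment. That rests on the text alone and on no numerical assumption. If recruited participants were used as the numerator, occurrence would be understated about threefold at the protocol's own 33% recruitment. The conflict between end of treatment and 12 months is likewise plain from the text, and the documents do not settle which was meant.

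The size of the risk-factor problem is conditional: at least 17 years at 1.5% recurrence and at most 75 participants a year, but 5.3 to 2.7 years at an assumed 5% to 10%. The supportable conclusion is that the recurrence assumption needs its own statement and that the regression should depend on the events seen.

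This should be corrected. The cohort is ancillary, and nothing here touches the randomised comparison.

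**What to change.** 1. **Objective and pilot rule.** Restate the cohort objective in the Trial Summary and section 1.2.1, and the pilot rule in Appendix A, as recurrence and quality of life among LTBI patients who have had DILI. Cost: wording only.

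2. **If occurrence is to be kept,** add two aggregate counts to the site screening log: LTBI treatment starts (denominator) and all DILI cases among them, including decliners and those not suitable for reintroduction (numerator). Cost: two numbers per site per reporting period, best collected prospectively from the start.

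3. **Time point.** Choose one time point for the cohort outcomes and use it in both the outcome lists and the Statistical analysis paragraph. If 12 months is chosen, state the origin from which it runs and add an EQ-5D-5L at that point; if end of treatment, the present schedule suffices.

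4. **Recurrence assumption and regression.** State the recurrence assumption separately from occurrence, with its basis or a range. Make the exploratory regression conditional on the number of recurrences observed; the protocol's 1300 implies about 20 for two factors. Recurrence with its 95% confidence interval, already planned, then stands as the main result whatever the number of events. Cost: wording only.

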# 1.2.3. Choice of treatment

Both regimens are accepted as standard of care in the NHS and globally. Based on weak evidence, one regimen may be associated with a lower DILI recurrence frequency but entails a longer total duration of treatment (9 months vs 6 months).

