## 2.2.2. Secondary

- Severity of DILI recurrence
- Reported clinical cure at end of treatment (EoT)
- Reported clinical cure at 12 months
- Total number of days on ATT at EoT
- ATT adherence at EoT
- Adverse event rate at 12 months
- Mortality at 12 months
- Quality of Life using EQ-5D and healthcare resource use

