# 8. Trial procedures and assessments

#### 8.1. Summary of assessments

A summary of trial procedures is shown in figure 2. A detailed description of each procedure can be found in section 8.2.

Figure 2: Summary of trial procedures time point

Trial	TB-DILI Trial	Protocol	1.2	date:	02-Aug-2022	Page 30 of 58
name:		version:				

															TRIAI	L PERI	OD						
TIMEPOINTS	E	R	Pha	ise A						Pha	se B				Phase	e C		DIL	Recurrence		ЕоТ		Follow- up Post R
Timepoint [Weeks]	W-2	W-1				W0				W1	W2	W4	W6	W8	W16	W24	W32	Diagnosis	2-Weeks after	W25	W33	*	W52
Timepoint [Days]		-1	0	1	3	4	6	7	9									of DILI	treatment re-start				
Tolerance [Days]	а	±2	±1	±1	±1	±1	±1	±1	±1	±4	±4	±4	±4	±4	±14	±14	±14	-	-	-	-		-
ENROLMENT:																							
Eligibility screen	Х																						
Informed consent	Х																						
Baseline Assessments																							
Adjudication panel confirmation	Х																	Х					
EQ-5D-5L	Х																						
Randomisation		Х																					
CONTROL ARM																							
Drug Re-Introdcution																							
Reintroduce EH				Х																			
Reintroduce R						Х																	
Reintroduce Z								Х															
Drug Discontinuation																							
Discontinue Z+R														Х									
Assessments																							
LFT (suggested not mandated)			х		х		х		х	х	х	x	x	x	x	x	x	х	х				
EQ-5D-5L			Х								Х							Х	Х	Х			Х
Follow-Up post EoT																							
Follow-up telephone call																				Х		Х	
INTERVENTION ARM																							
Drug Re-Introdcution																							
Reintroduce EH				Х																			
Reintroduce R						Х																	
Drug Discontinuation																							
Discontinue R														Х									
Assessments																							
EQ.5D-5L			Х						_	Γ.	Х							Х	Х		Х		Х
Follow-Up post EoT						CI 31				_					 								
Follow-up telephone call					ľ	5.510	[														Х	Х	

E = Enrolment

R = Randomisation

EoT = End of Treatment

a. The enrolment period will occur at the onset of DILI, the period between E & R will be variable dependent upon patient recovery. Predicted average time is 2 weeks

\* Every 12 weeks after EoT until 12 months post R

Trial	TB-DILI Trial	Protocol	1.2	date:	02-Aug-2022	Page 32 of 58
name:		version:				

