#### EoT

• EQ5D questionnaire is completed one week after the end of treatment: This is expected to be W25 for control arm and W37 for intervention arm

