# 10.6. Reporting period

Details of unexpected AEs (except those listed is section 10.1) will be documented and reported from the date of commencement of protocol defined treatment 12 months after randomisation. In the case where participants are still being treated at the 12-month follow-up, the reporting period will be extended to 3 months post the 12-month follow-up.

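### The adverse-event rate has two incompatible windows; the one in the Trial Summary is by design about 33–50% longer in the intervention arm

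*Protocol*

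**What the plan says.** The Outcome Measures entry of the Trial Summary lists "Adverse event rate at EoT or at 12 months whichever is sooner". The body of the protocol, section 2.2.2, lists the same outcome as "Adverse event rate at 12 months".

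Planned treatment lasts 9 months in the intervention arm and 6 months in the control arm (section 1.2.3). The EoT entry under section 9.1.4 places a questionnaire one week after treatment ends and says of its timing: "This is expected to be W25 for control arm and W37 for intervention arm". The schedule in section 8.1 has EoT columns at W25 for control but W33 for intervention. Follow-up calls in both arms continue "Every 12 weeks after EoT until 12 months post R".

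Section 10.1 makes the expected events of Table 4 secondary outcomes, to be collected on the eCRF. It gives no end date for that collection. Section 10.6 sets a reporting period that runs "from the date of commencement of protocol defined treatment 12 months after randomisation", and for participants still on treatment at that point "the reporting period will be extended to 3 months post the 12-month follow-up". It concerns unexpected events and excepts those listed in section 10.1.

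**The concern.** One outcome cannot end both at EoT and at 12 months. The choice matters because EoT is set by the allocated regimen. A window that stops at EoT observes the two arms for different lengths of time, so the comparison mixes tolerability with length of observation. The protocol defines an adverse event as not necessarily caused by treatment, and Table 4 includes headache, fever, malaise, nausea, joint pains and influenza, all of which also occur in people off treatment. Under the Summary's rule such events would be counted for longer in the intervention arm, and control-arm events in the months after EoT would be dropped. The stated aim is to compare the relative safety of two strategies, analysed by randomised allocation (sections 2.1 and 14.2.2). That fits a common window from randomisation better than one that depends on the arm.

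**Working it through.** **Window lengths.** Section 1.2.3 gives 9/6 months = 1.50. The EoT entry under section 9.1.4, less the one-week lag, gives (37 − 1)/(25 − 1) = 36/24 weeks = 1.50, so these two places agree. The schedule in section 8.1 gives (33 − 1)/(25 − 1) = 32/24 = 1.33. All these times precede 12 months, so on planned durations the 12-month cap does not operate and EoT sets the window. Follow-up left uncounted before week 52 is 52 − 24 = 28 weeks in control, against 52 − 36 = 16 weeks (or 52 − 32 = 20) in intervention. Under section 2.2.2 both arms have 52 weeks, a ratio of 1.00.

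**Proportion affected, equal constant hazard.** The protocol gives no adverse-event proportion, so the control proportion by week 24, P, is an assumption varied from 10% to 50%. With the same weekly hazard in both arms, on and off drug, the intervention proportion at its EoT is 1 − (1 − P)^r, where r is the window ratio.

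| Control by W24 (assumed) | Intervention, r = 1.50 | Ratio of proportions | Intervention, r = 1.33 | Ratio of proportions |
|---|---|---|---|---|
| 10% | 14.6% | 1.46 | 13.1% | 1.31 |
| 20% | 28.4% | 1.42 | 25.7% | 1.29 |
| 30% | 41.4% | 1.38 | 37.8% | 1.26 |
| 50% | 64.6% | 1.29 | 60.3% | 1.21 |

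**Proportion affected, early clustering.** The only timing figure in the protocol is for liver injury: 75–88% of episodes fall in the first 8 weeks (section 1.1). Borrow that as the share f of the 24-week cumulative hazard, with the remainder spread evenly over weeks 8–24 and continuing at that pace. Extending the window to week T multiplies the cumulative hazard by m = 1 + (1 − f)/16 × (T − 24).

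- T = 36: m = 1 + 0.25/16 × 12 = 1.19 (f = 0.75), or 1 + 0.12/16 × 12 = 1.09 (f = 0.88). From 30%, 1 − 0.70^m gives 34.5% or 32.2%, an excess of 4.5 or 2.2 points.
- T = 32: m = 1.125 or 1.06, giving 33.1% or 31.5%.

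**Events per person-time.** Under a constant hazard the rate ratio is 1.00. Under early clustering it is m/r: 1.19/1.5 = 0.79 and 1.09/1.5 = 0.73 for T = 36, or 1.125/1.33 = 0.84 and 1.06/1.33 = 0.80 for T = 32. These favour the intervention arm although the underlying hazards are the same.

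**Shift of EoT by recurrence.** Section 1.1 expects 28 days' delay per episode, and section 14.1.1 assumes recurrence in 10% and 1.5%. The mean difference is (0.10 − 0.015) × 28 = 2.4 days. It lengthens the control window and is negligible beside the 8 to 12 weeks between the planned EoT times.

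**The case against.** Section 2.2.2 already states the better window, so the fault may be no more than one line in a synopsis. That is fair as to the effort of repair, but both lines are current text. An SAP could choose between them; it could not make the protocol consistent.

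A reader might infer that the Summary's rule is sure to produce a large false excess of events in the intervention arm, 11 points or a ratio of 1.38. The documents do not support that. The figure needs an assumed 30%, a constant hazard that continues off drug, and a rate that means the proportion affected. Under early clustering the excess shrinks to a few points, and with person-time the bias is nil or reversed.

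Nor would every excess be an artefact. Many Table 4 events are drug effects, and section 14.2.2 takes the risk of treatment-related liver injury after stopping drugs as zero. For events that occur only on drug, more events over longer treatment are a true consequence of the regimen. With a constant on-drug hazard, a 12-month window would show the same 41% against 30%.

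It is also tempting to read section 10.6 as a third window for this outcome, or as proof that these events are captured to 12 months. It is neither, because it excludes the events listed in section 10.1.

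Finally, the protocol does not call this the main tolerability comparison. It is one of eight secondary outcomes, and liver safety is carried by the primary outcome with its own 12-month window. Leaving the definition of the rate to an SAP would be ordinary practice and is not in itself a fault.

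**Conclusion.** The contradiction stands. The Trial Summary and section 2.2.2 give one secondary outcome two windows, and the Summary's version observes the intervention arm about 50% longer on the durations in sections 1.2.3 and 9.1.4, or about 33% longer on the schedule in section 8.1. These ratios rest on planned durations; early stopping or prolonged treatment would alter them.

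The effect on the comparison is conditional. For a proportion or count, events that also occur off treatment would show an artefactual excess in the intervention arm, with ratios of about 1.46 to 1.29 at the 1.5 window ratio under the constant-hazard assumption, and much smaller ones if events come early. For a person-time rate the bias is absent or runs the other way. Since the protocol does not say which kind of rate is meant, even the direction is open. The primary outcome and the sample size are not touched.

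**What to change.** - Change the Trial Summary line to match section 2.2.2: one fixed window for the adverse-event rate, from randomisation to 12 months, in both arms.
- State in section 10.1 or 10.6 that the expected events of Table 4 are collected on the eCRF to 12 months in both arms. Section 10.6 does not say this at present.
- State, in the protocol or the SAP, whether the rate is the proportion affected, a count of events, or events per person-time. Any on-treatment person-time rate should be reported as supportive only.
- Reconcile the intervention arm's EoT timing between the schedule in section 8.1 (W33) and the EoT entry under section 9.1.4 (W37).

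The cost is a few lines of text and continued recording of listed events after EoT, which can use the telephone follow-up and 12-month data collection already planned for both arms.
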